8.5 Compensation

8.5.1 Subject

For both phases, subjects will be compensated for their travel expenses and spent time at the clinic with a [REDACTED] voucher at the end of each visit. If subjects come from more than 150 miles from the clinic, Össur will pay for requested mileage and be reimbursed as applicable ([REDACTED]).

8.5.2 Clinic

For the Clinical Testing activity, compensation for the orthopedic clinic will be according to the agreement made.

8.6 Responsibilities

Sponsor Coordinating/Principal Investigator (PI)

- Identify sites
- Train site staff on study procedures
- Collect Data
- Investigate possible vigilance cases/SAEs
- Monitor trial
- Technical support

Monitor

- Train site staff on study procedures
- Monitor trial
- Analyze results
- Write report

Sponsor Research Assistants (SRA)

- Technical support

Local Co-Investigator

- Collect data

Local Principal Investigator (LPI)

- Screen subjects
- Explain trial to participants
- Responsible for obtaining informed consent from test subjects
- Conduct all trial procedures at investigators' site
- Collect data
- Fit users with trial device and back to their current prosthesis
- Manage study documentation

8.7 Study monitoring and Oversight

The study monitor will ensure that all procedures are followed correctly and according to the study protocol. The study monitor will gather and review all study data and inform the LPI of missing data or nonconformities to the study protocol.

The study monitor and LPI will maintain communication on a minimum biweekly basis, via telephone and email. The LPI will provide the study monitor with information of all scheduled study visits. The study monitor will visit each investigational site at least once while a study visit takes place.

9 Investigational Device Accountability

The investigational devices will be provided as needed for the study population. Devices will not be packaged but will be labeled according to **FDA** regulatory requirements.

The **LPI** will keep records documenting the receipt, use and return of the investigational device in the Investigational Device Management Form, including:

- Date of receipt
- ID of each investigational device
- Date of use
- Subject ID
- Date of device return
- Date of return of unused, expired or malfunctioning investigational devices, as applicable

10 Statistical Considerations

10.1 Statistical design and procedures

Phase I

The dataset will be assessed with descriptive statistics only, comparing the means and variance for the two data points: prior-evaluation (current device with current firmware) and post-evaluation (investigational device with investigational firmware). Acceptance criteria for the data, as applicable, is defined in **Table 4 Endpoints, test methods and hypotheses**.

Phase II

The hypotheses (A1, A2, D, F, G, H, J) will be assessed with one sample binomial test. Other hypotheses will be tested using a two-tailed, paired, student's t-test (if the data are deemed to be normal) or using the Wilcoxon signed-rank test (if the data are deemed to be non-normal).

Subgroup analysis will not be performed as no subgroups are defined.

Repeated measures analysis has the advantage of increased power vis-à-vis group allocations and reduction in error variance associated with individual difference, as each subject acts as its own control. This is important for studying amputees as the group is a small proportion of the total population, and with specific inclusion/exclusion criteria the total eligible population becomes very small, making it difficult to find and recruit subjects to attain an acceptable level of power. This limited population pool often results in slightly heterogeneous sample, as the amputees available are few and far between, in every sense. Furthermore, no single amputation procedure and therefore amputated stump is exactly the same, making the experience of each amputee a bit unique. The within-subject design significantly reduces the individual differences when comparing the two conditions.

The drawback of the design is the potential of “carryover effects”, i.e. experience from one condition can affect outcome or performance in the other condition, creating a confounding extraneous variable that varies with the independent variable. Such effects are: practice, positive carryover effect to the latter condition; and fatigue, negative carryover effect to the latter condition

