A noticeable support of the swing phase in flexion and extension should be visible, plus a similar or an improved capacity at keeping up with the user in comparison to the current firmware. The dynamic of the swing phase while walking will be investigated via the 2MWT and 10mWT and potentially lead to similar or improved performance in comparison to the current firmware.

Concerning the sit-to-stand activities, time to perform the 5 times sit to stand test (5XSST) will be evaluated.

Similar as the previous tasks, stair ascent will be noticeable in the video documentation. In particular the subject will walk upstairs, stop and fully load the prosthetic knee. The time to perform the stair ascent will be documented and the performance will be evaluated with the Stair Assessment Index.

For each activity, the users will be asked to compare both firmware and rate on a worse, equal, better scale, if these tasks felt similar or different with the second firmware (without knowing which firmware is the updated one).

Additionally, feedback on the performance of the Pro-Flex Terra Foot and the POWER KNEE (phase I: with firmware 2, phase II: with updated firmware) will be collected.

The first phase can be repeated as many times as needed.

In phase II, the primary objective is to validate the firmware update.

The investigational device will be assessed with regards to its capability to be used with the indicated patient group, providing benefits to the subjects. No risks or anticipated adverse device effects (ADE) are to be assessed. The hypothesis and endpoints are specified in **Table 2**.

No claims are to be evaluated.

The following performance aspects are to be verified (relating to features in table 3 above):

- The investigational device provides perceived support to the user in sit to stand activities (Powered flexion and extension).
- The investigational device provides perceived support to the user in stand to sit activities (Controlled yielding).
- The investigational device provides natural speed adaptation within typical walking cadence, no perceived speed limit (Natural speed adaptation).
- The investigational device provides natural ambulation in stair ascent.

For all hypothesis:

μ_0 is average of measurements at baseline with the comparator (Power Knee with current marketed firmware);

μ_1 is the average of measurements with the investigational device (Power Knee with firmware update);

and $|M_{NI}|$ is the margin of non – inferiority

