and $|M_E|$ is the margin of equivalence

and P_r is the probability of a rating

Clarification: Phase I will include up to 10 subjects and will be conducted before the firmware is going through formal validation. Phase II will include up to 30 subjects and will be conducted to validate the firmware.

Table 4 Endpoints, test methods and hypotheses

	Hypothesis	Test Method	Endpoint	Acceptance Criteria for phase I	Acceptance Criteria for phase II	Limitations, comments
A1	Sit to stand activity is perceived as better and not worse with the firmware update compared to previous.	Rating: worse, same, better (1-3)	Rating score 1-3	In average no more than 22.5% of the subjects should rate the firmware update no worse.	$H_0: P_{worse} = 0,333$ $H_1: P_{worse} < 0,333$ ∧ $H_0: P_{better} = 0,333$ $H_1: P_{better} > 0,333$ $\forall p < 0,05$	
A2	Stand to sit activity is perceived as better and not worse with the firmware update compared to previous.	Rating: worse, same, better (1-3)	Rating score 1-3	In average no more than 22.5% subjects should rate the firmware update no worse.	$H_0: P_{worse} = 0,333$ $H_1: P_{worse} < 0,333$ ∧ $H_0: P_{better} = 0,333$ $H_1: P_{better} > 0,333$ $\forall p < 0,05$	
B	Mobility is no worse with the firmware update compared to previous.	10mWT	Time in seconds	Exploratory	No significant increase in time needed to perform the 10mWT with the firmware upgrade. $H_0: \mu_0 - \mu_1 \geq M_{NI} $ $H_1: \mu_0 - \mu_1 < M_{NI} $ $M_{NI} = MDC$ $MDC = 0,13 \text{ m/s}^{13}$ $p < 0,05$	To be able to check if the knee keeps up with the user in a better way. Sensors logging
C	Mobility is no worse with the firmware update compared to previous.	2MWT	Distance in meters	Exploratory	No significant reduction in distance walked on 2MWT with the firmware upgrade. $H_0: \mu_0 - \mu_1 \geq M_{NI} $ $H_1: \mu_0 - \mu_1 < M_{NI} $ $M_{NI} = MDC$ $MDC = 34 \text{ m}^{14}$ $p < 0,05$	Sensors logging
D	Users perception of level-ground walking is no worse with the firmware update compared to previous.	Rating: worse, same, better (1-3)	Rating score 1-3	In average no more than 22.5% of the subjects should rate the firmware update no worse.	$H_0: P_{worse} = 0,333$ $H_1: P_{worse} < 0,333$ ∧ $H_0: P_{better} = 0,333$ $H_1: P_{better} > 0,333$	

					$\forall p < 0,05$	

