E	The PK firmware update shows no worse results in stair ascent activities compared to previous.	Stair assessment index	Rating score 1-13	Exploratory	$H_0: \mu_0 - \mu_1 \geq M_{NI} $ $H_1: \mu_1 - \mu_0 < M_{NI} $ $M_{NI} = 1$ point $p < 0,05$	Sensors logging ICCs of rs = 1.00 (p < 0.001) ¹²
F	Users perception of stair ascent is no worse with the firmware update compared to previous.	Rating: worse, same, better (1-3)	Rating score 1-3	Exploratory	$H_0: P_{worse} = 0,333$ $H_1: P_{worse} < 0,333$ \wedge $H_0: P_{better} = 0,333$ $H_1: P_{better} > 0,333$ $\forall p < 0,05$	
G	Users perception of exiting from stair ascent mode is no worse with the firmware update compared to previous.	Rating: worse, same, better (1-3)	Rating score 1-3	Exploratory	$H_0: P_{worse} = 0,333$ $H_1: P_{worse} < 0,333$ \wedge $H_0: P_{better} = 0,333$ $H_1: P_{better} > 0,333$ $\forall p < 0,05$	
H	Users perception of entering stair ascent mode is no worse with the firmware update compared to previous.	Rating: worse, same, better (1-3)	Rating score 1-3	Exploratory	$H_0: P_{worse} = 0,333$ $H_1: P_{worse} < 0,333$ \wedge $H_0: P_{better} = 0,333$ $H_1: P_{better} > 0,333$ $\forall p < 0,05$	

Secondary

I	Exiting stair ascent mode with the firmware update reduces unexpected movements compared to previous.	2 repetitions of Stair ascent	Count of unexpected movements	Exploratory	Significant reduction in unexpected movements when exiting stair ascent: $H_0: \mu_0 - \mu_1 \leq 0$ $H_1: \mu_0 - \mu_1 > 0$ $p < 0,05$	
J	Users perception with Power Knee and Pro-Flex Terra is no worse	Rating: worse, same,	Rating score 1-3	Firmware 2 will be tested: In average no more than 22.5%	Updated firmware will be tested : $H_0: P_{worse} = 0,333$	Sensors logging Activities :

	compared to the combination of the Power Knee and the prescribed foot.	better (1-3)		of the subjects should rate the combination no worse.	$H_1: P_{worse} < 0,333$ \wedge $H_0: P_{better} = 0,333$ $H_1: P_{better} > 0,333$ $\forall p < 0,05$	Walking on level ground (SSWS, slow and fast) Sit to stand and stand to sit Stair ascent and descent Ramp ascent and descent Squatting
--	--	--------------	--	---	--	--

Exploratory

K	Amount of time needed to perform 5XSST	5 times sit to stand test	Time in seconds			
L	Temporal spatial parameters during 5XSST	Moticon Insoles Xsens Optogait	Temporal spatial parameter s			
M	Temporal spatial parameters during 2MWT	Moticon Insoles Xsens Optogait	Temporal spatial parameter s			

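### Section 10.1 gives endpoints B, C and E a two-tailed paired test without tying it to Table 4's non-inferiority margins; rows B and C add a conflicting criterion, and row B sets seconds against m/s

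*Combined protocol and SAP*

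**What the plan says.** Section 10.1 (Phase II) gives a one-sample binomial test to A1, A2, D, F, G, H and J. For everything else, "Other hypotheses will be tested using a two-tailed, paired" t-test applies if the data are deemed normal, and a Wilcoxon signed-rank test if not. B, C and E fall in this group. Section 10.2 sends the reader to Table 4 for pass/fail.

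In the Phase II column of Table 4:
- **Row B (10mWT).** The endpoint is "Time in seconds". The criterion opens with "No significant increase in time needed to perform the 10mWT with the firmware upgrade", followed by hypotheses against M_NI = 0.13 m/s.
- **Row C (2MWT).** The endpoint is distance in metres. The criterion opens with "No significant reduction in distance walked on 2MWT with the firmware upgrade", followed by hypotheses against M_NI = 34 m.
- **Row E (Stair Assessment Index).** The claim is "The PK firmware update shows no worse results in stair ascent activities compared to previous". The row gives only hypotheses, against M_NI = 1 point. Its H0 uses μ0 − μ1 and its H1 uses μ1 − μ0.
- All three rows give p < 0.05 without saying whether it is one- or two-tailed.

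Section 7 says that μ0 "is average of measurements at baseline with the comparator (Power Knee with current marketed firmware"), so μ1 is the update. It also defines a second quantity that "is the margin of equivalence", which no row of Table 4 uses.

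**The concern.** A two-tailed paired test with no stated null is normally run against zero. A non-inferiority claim needs a test against the margin. The documents do not say which one decides B, C and E.

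The pointer to Table 4 does not settle this, because rows B and C contain both ideas. Row I shows how the table uses such lines: there, "Significant reduction in unexpected movements when exiting stair ascent" sits above hypotheses whose null is zero. The parallel lines in B and C therefore suggest a zero null, while the hypotheses beneath them use a margin.

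Two analysts could follow the text faithfully and report opposite verdicts on the same data. These rows stand above the Secondary heading of Table 4, in the phase meant to validate the firmware.

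**Working it through.** **The plan's own figure.** The section 10.2 calculation reproduces. With X ~ Bin(15, 0.6666), P(X ≥ 14) = 0.01939. With p = 0.6666 + 0.2834003 = 0.9500003, P(X ≥ 14) = 0.8290. The smallest adequate n is 15. This covers the binomial endpoints only; no calculation is given for B, C or E.

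**Inputs.** n = 15 (minimum completers, section 8.3) and n = 30 (cap, section 8.2). Margins M are from Table 4. The documents give no SD of paired differences, so every SD below is an assumption. If MDC means 1.645 or 1.96 times the SD of test-retest differences, the SD is 34/1.645 = 20.7 m or 34/1.96 = 17.3 m for C, and 0.079 or 0.066 m/s for B. Loss is current minus update. t(0.975) is 2.1448 at n = 15 and 2.0452 at n = 30.

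**One data set, two verdicts (row C, n = 15, mean loss 12 m, SD 17.3 m).** SE = 17.3/√15 = 4.467.
- Against zero: t = 12/4.467 = 2.686, two-tailed p = 0.018. This is a significant reduction, so C fails.
- Against the margin: t = (12 − 34)/4.467 = −4.93, one-sided p = 0.0001. The 95% CI for the loss is 2.4 to 21.6 m, so C passes.

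**Range of disagreement for C.** Observed losses between t·SD/√n and 34 − t·SD/√n are significant yet non-inferior:

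| SD (m) | n = 15 | n = 30 |
|---|---|---|
| 17.3 | 9.6 to 24.4 m | 6.5 to 27.5 m |
| 20.7 | 11.4 to 22.6 m | 7.7 to 26.3 m |

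**How often.** This was simulated with 400,000 trials per case. It depends only on SD/M (0.608 or 0.510), so it applies to C and to B analysed as speed. At a true loss of M/2 (17 m or 0.065 m/s), verdicts are opposite in 68% or 88% of trials at n = 15, and 98% or 99.9% at n = 30. M/2 is the peak. At n = 15 the rate is 31% or 42% at M/4 and 2.5% at zero true difference.

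**The other direction.** Under the reading that a non-significant result passes, the false-pass rate at a true loss of M is P(T < t(0.975)) with noncentrality √n·M/SD. At the MDC-consistent SDs it is below 0.01% at n = 15. For larger assumed SDs, B as speed gives:

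| SD (m/s) | n = 15 | n = 30 |
|---|---|---|
| 0.07 | <0.1% | <0.1% |
| 0.13 | 5% | <0.1% |
| 0.20 | 35% | 7% |
| 0.26 | 56% | 25% |

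It exceeds 2.5% only if the SD is above 0.119 m/s (n = 15) or 0.176 m/s (n = 30). For C the thresholds are 31.2 m and 45.9 m.

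**Row B units.** Over an assumed 10 m, a speed loss of 0.13 m/s from speed v adds 10/(v − 0.13) − 10/v seconds: 4.61 s at 0.6 m/s, 1.49 s at 1.0 m/s and 0.73 s at 1.4 m/s. No single margin in seconds follows.

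**Row B sign, as printed.** On the time scale, slowing from 10 s to 14 s gives μ0 − μ1 = −4 s and meets H1. Speeding up from 10 s to 8 s gives +2 s, which exceeds 1.49 s and falls under H0.

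**The case against.** The strongest reply is that section 10.1 says the hypotheses will be tested, the hypotheses are those in Table 4, and a paired t-test can be run against a shifted null. On this reading the margin is not dropped, and the lines in B and C are loose captions. That is a fair reading, and row C's margin test can indeed be run as printed. But it is not the only reading, and row I's usage supports the other.

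The sign points may be extraction artefacts, since absolute-value bars may have been lost from the table. That caveat stands for row B's direction and row E's mismatch. Bars around the differences would turn these into equivalence hypotheses, which fits neither the no-worse claims nor the use of M_NI. The unit mismatch and the silence of 10.1 do not depend on the bars.

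Section 8.4 refers to Annex 17.4 for the functional tests and allows timing gates that record speed. The annex is not in the supplied text and might define a conversion. Table 4 itself gives none.

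Two points on size also stand. The 68% to 99.9% figures are at the point of maximum disagreement. At MDC-consistent SDs the zero-null rule is the stricter one, so the likelier error is failing an acceptable update. Finally, section 8.1 names general usability as the primary endpoint and places the Table 4 items under secondary endpoints, so the exact weight of B, C and E is unclear.

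**Conclusion.** The concern holds and should be fixed before Phase II data are analysed. Three parts rest on the text alone: 10.1 names no margin for B, C or E; rows B and C carry a line that can contradict their own margin hypotheses; and row B's endpoint and margin are in different units, so it cannot be tested as printed.

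The size of the conflict rests on assumed SDs. With MDC-consistent SDs it is large for moderate true losses and small near zero difference, and it runs towards wrongly failing the update. A substantial risk of passing a worse update needs much larger SDs: the 35% and 56% figures for B at n = 15 require 1.5 and 2 times the margin. No false-pass rate is claimed for E, whose row states only margin hypotheses. The 0.025 in section 10.2 belongs to the binomial calculation and is not in conflict here; for B, C and E the open question is the sidedness of p < 0.05.

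**What to change.** - **Section 10.1.** For B, C and E define loss as current minus update. Declare non-inferiority only if the upper limit of the two-sided 95% CI for the mean paired loss is below M_NI. This is one-sided 0.025, which matches a two-tailed test at p < 0.05.
- **Non-normal data.** Apply the signed-rank test to loss minus M_NI, and state how zeros are handled. This matters for E, where a loss of exactly 1 point becomes a zero. With 9 subjects unchanged, 5 losing 1 point and 1 losing 3 points, the exact one-sided p is 0.046 with zeros dropped and 0.011 with Pratt ranks. Pratt ranks with exact p-values are one suitable choice.
- **Rows B and C.** Delete the opening lines about significance.
- **Row B.** Analyse speed (distance divided by time), which corrects unit and sign together.
- **Row E.** Write H1 as μ0 − μ1 < M_NI, and state which direction of the index is better.
- **Section 10.2.** State that the 15-subject calculation covers only the binomial endpoints.

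No new measurements are needed. The edits touch endpoints, so they go through the amendment review in section 11.1. The plan would also have to acknowledge that power for B, C and E is not established. At zero true difference and n = 15 it is above 99.9% for B and C with MDC-consistent SDs, but 65% or 44% for B at an SD of 0.20 or 0.26 m/s.

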8.1 General

The test will be a randomized, controlled, double-blinded, cross-over investigation for both phases I and II.

Amputees are a small proportion of the general population. The population group specified in the inclusion/exclusion criteria is a further subsample of amputees. For practical reasons, i.e. to achieve statistical power, it is therefore more feasible to use within-subject comparison rather than creating study arms to compare. The results of the phase I data collection will be used subsequent to first testing, to further improve the tested device, i.e. PKM. Furthermore, as mobile amputees generally have and use a prosthetic device for their daily activities, within-comparison is feasible comparing to the subjects previous device.

All investigational activities will be conducted at prosthetic out-patient clinics.

As stated above the primary endpoint is the general usability of the Power Knee Firmware Update in ADLs, which are specifically explained in the secondary endpoints are (see **Table 4**) in that respective order of significance. See previous chapter on objectives and hypothesis and **Table 4** for rationale.

Drop-outs and withdrawals may be replaced if deemed necessary to fulfil the methodological standards of the study.

Instruments for data collection will include the following:

2MWT: 2-minute walk test

10mWT: 10-meter walk test

5XSST: 5 times sit-to-stand test

Specific questionnaire: In-house generated questionnaire on specific features in the investigation device.

Video

Data logging by Ossur Logic/ Ossur Toolbox

See chapter **10.2 Sample size calculation**.

Equipment required for each subject:

- Detailed protocol
- Chair with Armrests for 5XSST
- Measuring tape
- Markers and a measure corridor/course of known distance for 2MWT and 10mWT
- Video camera for video documentation
- PC to read out Ossur Logic and Ossur Toolbox results
- Case report forms (CRFs) – Tablet/computer OR printed out case report forms
- Investigational device: POWER KNEE with the Firmware Update
- POWER KNEE with the current marketed firmware
- Pro-Flex Terra feet
- Other components as applicable (pylons and adapters for fitting)
- Tools for fitting
- LASAR Posture equipment for alignment
- Xsens (Annex 17.5.1)
- Moticon Insoles (Annex 17.5.2)

- Optogait (Annex 17.5.3)
- Microgate Witty Timing Gate (Annex 17.5.4)

The equipment used does not require specific monitoring, or maintenance.

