8.4 Procedures

i) Recruitment

Potential subjects will be identified by using the investigation sites' existing database of patients, or from Össur's customer database. Participants may be also recruited from external clinics and customers, through word of mouth, or during customer representative meetings where Össur representatives engage with users and clinicians. Customer representatives, who have prior experience interacting with and servicing patients, will evaluate if a potential participant is cognitively capable of participating in the study. Based on their assessment, the customer representative will inform the LPI of the potential subject and provide their contact information.

The LPI or PI will establish communication with potential participants and provide information about the investigation.

If a potential participant meets the inclusion and exclusion criteria, the LPI or the PI will contact them via telephone. During this call, the LPI or PI will:

- Verify the participant's interest in the study.
- Provide detailed information about the study and potential risk of participating in the investigation
- Answer questions related to the study.
- Conduct a preliminary screening to assess eligibility.

The LPI or PI will communicate to the study monitor the number of users he has identified that meet the inclusion criteria and are willing to participate.

ii) Test procedure

For **both phases**, at the beginning of the visit, a researcher qualified to obtain informed consent will explain the study to the subject and proceed as described in chapter 13.8 Informed consent.

The users will be fitted with the Power Knee device in a combination with an Össur foot. If the prescribed foot is an Össur foot, it will be used for the test. If the prescribed foot is not an Össur foot, then Pro-Flex LP will be provided for the test.

Configuration phase:

Both the current marketed firmware and the updated firmware will be optimally configured for each user.

This configuration will be carried out by the research engineers (Group 1), who will not participate in the evaluation phase to ensure blinding.

Randomization:

Once optimal configuration is achieved for both firmware versions, users will be randomized into two groups:

- Group A will start activity blocks with the current marketed firmware.
- Group B will start activity blocks with the Power Knee Firmware Update.

Evaluation phase:

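### The Phase II tests ignore the randomised firmware order although section 10.1 warns of practice and fatigue, and no A/B balance is specified

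*Combined protocol and SAP*

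**What the plan says.** Section 8.1 describes the design: "The test will be a randomized, controlled, double-blinded, cross-over investigation for both phases I and II". In section 8.4, "users will be randomized into two groups", which differ only in which firmware comes first: Group A starts with the marketed firmware, and "Group B will start activity blocks with the Power Knee Firmware Update". No ratio, block size or other balancing rule is given.

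For Phase II, section 10.1 states: "The hypotheses (A1, A2, D, F, G, H, J) will be assessed with one sample binomial test". For the rest: "Other hypotheses will be tested using a two-tailed, paired, student's t-test (if the data are deemed to be normal", with the Wilcoxon signed-rank test as the alternative. Neither test has a period or sequence term. The section then names the drawback of the within-subject design: "Such effects are: practice, positive carryover effect to the latter condition; and fatigue, negative carryover effect to the latter condition". The text stops there, with no model term, stratification or sensitivity analysis. Sections 10.2 and 10.3 add nothing on order.

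Two further passages matter. Chapter 7 words the user's rating as "if these tasks felt similar or different with the second firmware", so it is a second-versus-first comparison that must be recoded to update versus current. Section 8.4 lets activity blocks be skipped, and section 10.3 analyses drop-outs for the procedures they completed. The A/B split can therefore differ by endpoint even if enrolment is balanced.

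**The concern.** In a two-period crossover, a general practice or fatigue effect moves the update-minus-current difference one way in Group A and the other way in Group B. A test that pools the groups treats this systematic contrast as noise. If the groups are equal, the estimate is unbiased but its standard error is too large, so the test is conservative and loses power. If they are unequal, part of the period effect stays in the estimate. The sponsor could then pass an update that is no better, or fail a sound one.

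For the ratings, a tendency to prefer whichever firmware came second counts for the update in Group A and against it in Group B. It cancels only when the groups are equal.

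**Working it through.** **The plan's own figure.** Section 10.2 takes p0 = 0.6666 and g = 0.2834003, so p1 = 0.95. With N = 15 and a critical count of 14, the exact binomial gives P(X ≥ 14 | p0) = 0.01939 and P(X ≥ 14 | p1) = 0.82905. Both match the stated values. Order does not enter this calculation.

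**Paired endpoints (B, C, E, I).** The documents give neither the SD of the paired differences nor a period effect, so the values below are assumptions. Write d = τ + sπ + e. Here s = +1 if the update is second (Group A) and −1 if it is first (Group B), e has SD 1, and π is the period effect in those SD units.

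- Bias of the plain mean: (2f − 1)π, where f is the share in Group A. At 20/10 or 10/5 this is 0.33π; at 8/7 it is 0.07π.
- Expected inflation of the sample variance: 1 + π² × 4·nA·nB / [n(n − 1)]. At 15/15 with π = 0.5 this is 1 + 0.25 × 900/870 = 1.26. With π = 1 it is 2.03.

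The table gives simulation results for the two-sided paired t-test at 0.05, with τ set so that power is 0.80 when π = 0. A positive π favours the second firmware and a positive τ favours the update. Where Table 4 uses a non-inferiority margin, read τ as the distance from the null value.

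| Split A/B | π (SD) | Bias (SD) | Type I error, planned | Rejection at τ, planned | Power with sequence |
|---|---|---|---|---|---|
| 15/15 | 0.25 | 0 | 0.044 | 0.78 | 0.80 |
| 15/15 | 0.5 | 0 | 0.029 | 0.72 | 0.80 |
| 15/15 | 1 | 0 | 0.006 | 0.50 | 0.80 |
| 8/7 | 0.5 | 0.03 | 0.031 | 0.76 | 0.79 |
| 7/8 | 0.5 | −0.03 | 0.030 | 0.68 | 0.79 |
| 10/5 | 0.5 | 0.17 | 0.062 | 0.89 | 0.75 |
| 20/10 | 0.5 | 0.17 | 0.101 | 0.93 | 0.75 |

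The high rejection rates in the last two rows come from bias, not real power. With the imbalance reversed, they fall to 0.51 (5/10) and 0.40 (10/20). The sequence-adjusted test holds type I error at about 0.05 in every case.

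Under simple 1:1 randomisation (assumed), the chance of a 10/5 split or worse in either direction is 0.30 at n = 15. The chance of 20/10 or worse is 0.10 at n = 30.

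**Ratings (A1, A2, D, F, G, H).** Assume no firmware effect, with 1/2 of users preferring the second firmware, 1/3 rating them the same and 1/6 preferring the first. Then P_better = f/2 + (1 − f)/6. This is 0.333 at f = 1/2 and 0.389 at f = 2/3. Against 0.333 at p < 0.05, Table 4 needs at least 9 better and at most 1 worse at n = 15, or at least 15 better and at most 5 worse at n = 30. Exact calculation, summing over splits with at least two thirds in Group A:

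| | n = 15 | n = 30 |
|---|---|---|
| Chance of such a split | 0.15 | 0.05 |
| P_better test alone passes | 8.6% | 15.4% |
| Both tests pass, as Table 4 requires | 1.6% | 4.7% |
| Both pass, no order preference | 0.4% | 0.9% |

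The error is not widened here. At 15/15 the variance of the better count is 15 × 1/2 × 1/2 + 15 × 1/6 × 5/6 = 5.83, against 30 × 1/3 × 2/3 = 6.67 with no order preference.

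**The case against.** The strongest reply is that randomising the order already protects the comparison. That is true on average. Over all simple 1:1 allocations the unadjusted estimate is unbiased and the paired test's type I error is about 0.05. Under the ratings scenario each user's chance of rating the update better averages (1/2 + 1/6)/2 = 1/3, so the joint pass rate stays at 0.4% and 0.9%. The bias is conditional on the split that occurs. It remains relevant because that split will be known at analysis and can be corrected.

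Second, the size of the power loss is assumed. The plan calls these effects potential, compares the firmwares back to back within each activity block, and recruits people who use or have tried the Power Knee. A small period effect is plausible, and at 0.25 SD the loss is only about 0.02. The 0.80 baseline is also hypothetical, since the only power calculation is for the binomial test.

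A reader might infer more than the documents support:

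- That the rating endpoints would falsely pass at the P_better rates. Table 4 also requires the P_worse test to pass.
- That period effects widen the error for the ratings. They do not.
- That J is affected. In Phase II it compares feet on the updated firmware, so the A/B order is not its contrast.
- That the N of 15 is wrong on this account. It is not.

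**Conclusion.** The omission is real: the plan randomises order, warns of order effects, and then neither analyses by order nor specifies balance. For B, C, E and I the cost is lost power under near-balance and conditional bias under imbalance. On the assumptions above, power at 15/15 falls from 0.80 to 0.78, 0.72 or 0.50 for period effects of 0.25, 0.5 or 1 SD. For A1, A2, D, F, G and H the harm is bias under imbalance only. In the scenario examined it raises the joint false-pass rate from under 1% to 1.6% (n = 15) or 4.7% (n = 30), given a split that is itself uncommon. This is an inexpensive gap to close; it does not invalidate the design.

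**What to change.** - Randomise A/B 1:1 in permuted blocks and state this in section 8.4. Balance also protects the adjusted test, whose power drops from 0.79 at 8/7 to 0.75 at 10/5 and 0.69 at 11/4.
- For B, C, E and I, analyse the within-subject difference with sequence in the model (the AB/BA crossover t-test, which averages the two sequence means with equal weight), or use a rank test stratified by sequence.
- For A1, A2, D, F, G and H, recode each rating to update versus current, tabulate by sequence, and base the test on the equally weighted average of the Group A and Group B proportions. The SAP should name the method used for its p-value. Do this per endpoint, since skipped blocks can unbalance a split that was even at enrolment.

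The cost is one degree of freedom in the paired analyses, a blocked list and SAP wording, with no extra subjects or procedures. The change removes period effects common to both firmwares. It does not remove carryover that differs between them, and the report should say so.
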